10.1.3.1.1 Serious Adverse Events

Serious Adverse Event Definition

An SAE is any untoward medical occurrence or effect that, at any dose,

- Results in death.
- Is life-threatening. (An AE is life-threatening if the patient was at immediate risk of death from the event as it occurred, i.e. it does not include a reaction that might have caused death if it had occurred in a more serious form.)
- Requires or prolongs inpatient hospitalisation. (Complications occurring during hospitalisation are AEs and are SAEs if they cause prolongation of the current hospitalisation. Hospitalisation for elective treatment of a pre-existing non-worsening condition is not, however, considered an AE. The details of such hospitalisations must be recorded on the medical history or physical examination page of the eCRF.)
- Results in persistent or significant disability/incapacity. (An AE is incapacitating or disabling if it results in a substantial and/or permanent disruption of the patient's ability to carry out normal life functions.)
- Results in a congenital anomaly/birth defect.

In addition, medical and scientific judgement is required to decide if prompt notification is required in situations other than those defined for SAEs above. This may include any event that the investigator regards as serious that did not strictly meet the criteria above but may have jeopardised the patient or required intervention to prevent one of the outcomes listed above, or that would suggest any significant hazard, contraindication, side effect, or precaution that may be associated with the use of the investigational product.

Note that if DC cardioversion is performed as indicated in the schedule of assessments (Section 8.1.2), it should not be reported as AE/SAE.

Reporting of Serious Adverse Events

Any SAE must be reported by the investigator if it occurs during the clinical study from signing of the ICF or within 30 days of receiving the study drug, whether or not the SAE is considered to be related to the investigational product. An SAE report consists of the SAE form. A copy of these forms must be faxed **within 24 h** for the attention of the product safety scientist at

Syneos Health Safety and Pharmacovigilance Department
[contact] or
Email: [contact]

The investigator should not wait to receive additional information to document the event fully before notification of an SAE, though additional information may be requested. Where applicable, information from relevant laboratory results, hospital case records, and autopsy reports should be obtained.

Instances of death, congenital abnormality, or an event that is of such clinical concern as to influence the overall assessment of safety, if brought to the attention of the investigator at any time after cessation of study drug administration and linked by the investigator to this study, should be reported to the study monitor.

Acesion Pharma and/or Syneos Health will promptly notify all relevant investigators and the regulatory authorities of findings that could adversely affect the safety of patients, impact on the conduct of the study, or alter the independent ethics committee (IEC) approval/favourable opinion of the study. In addition, Syneos Health, on behalf of Acesion Pharma, will expedite the reporting to all concerned investigators, to the IECs, where required, and to the regulatory authorities of all adverse reactions that are both serious and unexpected.

Reporting of Pregnancies

All pregnancies that occur in a patient or patient's partner during the study will be reported using a separate pregnancy reporting form. Reporting follows the same process as described above for SAE reporting. If there is also an SAE reported or suspected, an SAE form should also be completed and sent to the Syneos Health Safety and Pharmacovigilance Department as described above.

Further details of the procedures to be followed if a pregnancy occurs are provided in [Section 8.3.4.2](#).

10.1.3.1.2 Unexpected Adverse Reactions

Unexpected Adverse Reaction Definition

An unexpected adverse reaction is any untoward and unintended response that is related to the administration of the study drug at any dose that is not consistent with the applicable product information (e.g. investigator's brochure for an unauthorised investigational medicinal product or summary of product characteristics for an authorised product).

All suspected unexpected serious adverse reactions (SUSARs) will be the subject of expedited reporting. Only SUSARs assessed to be possibly, probably, or very

likely/certainly related to study drug are considered to have a reasonable causal relationship to study drug and are subject to reporting to regulatory authorities.

Acesion Pharma and/or Syneos Health shall ensure that all relevant information about a SUSAR that is fatal or life-threatening is reported to the relevant competent authorities and IEC within 7 days after knowledge by Acesion Pharma of such a case and that relevant follow-up information is communicated within an additional 8 days. All other SUSARs will be reported to the relevant competent authorities and IEC within 15 days after knowledge by Acesion Pharma of such a case. All investigators should follow SUSARs until the event is resolved or until, in the opinion of the investigator, the event is stabilised or determined to be chronic. Post-study SUSARs that occur after the patient has completed the clinical study must be reported by the investigator to Acesion Pharma.

Warnings and Precautions

There are no specific warnings associated with AP30663 administration.

Precautions to avoid local infusion site reactions are described in [Section 8.4.1](#).

Please refer to the most current version of the investigator's brochure for warnings and precautions.

10.1.3.2 Clinical Laboratory Evaluation

The haematology and clinical chemistry laboratory analyses will be performed at local laboratories. Reference ranges will be supplied by local laboratories and used by the investigator to assess the laboratory data for clinical significance and pathological changes. The following laboratory safety tests will be performed at the times outlined in the Schedule of Assessments in [Section 8.1.2](#).

The total amount of blood to be taken during the study from screening until the end of the 30-day study period amounts to a maximum of 131 mL (including blood samples for PK analyses). See [Section 17.2](#) for an overview of blood samples and volumes collected.

Haematology

Haemoglobin, haematocrit, red blood cells (erythrocytes), white blood cells (leukocytes, total and differential), basophils, eosinophils, lymphocytes, monocytes, neutrophils, and platelets.

Clinical Chemistry

ALT, AST, bilirubin, creatinine, gamma-glutamyltransferase, glucose (random), eGFR, urea (BUN), sodium, potassium, calcium, and magnesium.

Other Laboratory Variables

INR/APTT and TSH

10.1.3.3 Vital Signs

Vital signs will be recorded as indicated in the Schedule of Assessments in [Section 8.1.2](#). They will include BP, heart rate, and heart rhythm (from ECG) and will be recorded in a standardised manner, i.e. after the patient has rested in the (semi)supine position for 5 min and before blood sampling or laboratory tests. Vital signs measurements will be repeated in case of clinically significant abnormalities.

10.1.3.4 Physical Examination and Brief Physical Examination

At screening, weight and height will be recorded and a physical examination will be performed, followed by a brief physical examination at baseline (pre-infusion on Day 1) and Day 30. Any changes from the screening and baseline visit to Day 30 will be recorded. Full and brief physical examination will include the following assessments:

Table 3 Physical Examination

Assessment	Full physical examination	Brief physical examination
General appearance	X	x
Head, ears, eyes, nose, throat	X	-
Cardiovascular	X	x
Respiratory	X	x
Gastrointestinal	X	x
Dermatological	X	-
Neurological	X	-
Musculoskeletal	X	-
Lymphatic	X	-
Other (at the investigator's discretion)	X	x

10.1.3.5 Electrocardiogram

10.1.3.5.1 12-lead Digital Electrocardiogram

A 12-lead digital ECG will be performed at the times outlined in the Schedule of Assessments in [Section 8.1.2](#) in a standardised manner (i.e. after the patient has rested in the [semi]supine position for at least 5 min).

The investigator will assess ECG abnormalities (e.g. ischaemia, conduction abnormalities, and rhythm abnormalities) and define the ECG intervals as part of the

screening of eligibility and according to the inclusion/exclusion criteria, and as part of an adverse event assessment.

The following measurements will be provided for all PK time points: RR, PR, QRS, QT, QTcF (Fridericia's correction of QT interval), QTcB (optional), heart rate, as well as T- and U-wave morphology classifications.

Bedside safety ECGs will be collected by the site, printed and reviewed by the investigator on site.

ECG intervals based on these safety ECGs will only be recorded if part of an adverse event.

10.1.3.5.2 Telemetry

Heart rhythm will be recorded by telemetric monitoring as outlined in the Schedule of Assessments in [Section 8.1.2](#). Lead positioning on the patient for telemetric monitoring will be performed per local standards and local requirements of the telemetry equipment. During the 8 h post-infusion of study drug, the patient will remain under continuous medical observation. Should any significant heart rhythm changes occur during this observation, the recording from telemetry should be printed out, assessed for clinical significance, and recorded in the eCRF.

10.1.3.5.3 Holter Recording

A Holter recording will be performed the first 8 hours after infusion start for efficacy assessments and evaluated centrally as outlined in [Section 10.1.1.1](#). Sites will be contacted by email or telephone if clinical alerts have been detected on the extracted ECG or Holter reports overread by the central ECG laboratory.

Holter data will be retained in case additional retrospective analysis should be necessary for safety.

10.2 Independent Data Monitoring Committee

Safety, tolerability, PK/PD and efficacy will be regularly reviewed by an unblinded independent DMC to advise on dose escalation, de-escalation, and study progression decisions at the interim analyses. The DMC will also periodically review accumulating safety, tolerability, efficacy and PK/PD data throughout the study.

At the end of Part 1, after up to 36 initial patients receiving AP30663 and placebo have completed Day 2 assessments of the study (or terminated the study), the DMC will be convened to review the accumulating unblinded efficacy (including ECG and Holter ECG), PK/PD, safety and tolerability data for the study in an interim analysis, and provide a recommendation on dose escalation, de-escalation, and study progression/early termination in case there is a concern regarding safety (see [Section 8.1](#)

for options regarding Part 2 study design). A pre-determined efficacy algorithm will be put in place to guide the independent DMC in its decision. Decision rules will be based on the AF conversion rate, safety and tolerability signals including but not limited to increase in QTcF interval and number and severity of local injection site reactions.

During the enrolment period, an IA may be planned on a reduced cohort if preliminary blinded safety and efficacy data indicate that current enrolment is sufficient for the DMC to provide a recommendation for Part 2.

Full details of composition, operational aspects, and data to be reviewed and recommendations to be made by the DMC will be described in the DMC Charter. Detailed decision rules will be outlined in the DMC Charter or the SAP.

10.3 Appropriateness of Measurements

The efficacy and safety assessments planned for this study are widely used and generally recognised as reliable, accurate, and relevant to the disease condition.

11 STATISTICAL METHODS

11.1 Statistical and Analytical Plans

The statistical analysis will be performed using SAS® version 9.4 or higher. The main population for efficacy analysis will be the Full Analysis Set; supportive analyses will also be performed using the Per-Protocol Set.

Continuous data will be presented using descriptive summaries (e.g. mean, standard deviation [SD], minimum, maximum, median, lower quartile, and upper quartile). Categorical variables will be presented by the number of observations and relative (%) frequency.

Unless otherwise stated, the baseline value for any variable will be the last non-missing value taken prior to the infusion of the double-blind study treatment on Day 1. Pre-infusion Day 1 assessments will be included in this derivation of baseline.

Unless otherwise stated, all statistical tests will be 2-sided and conducted at the 5% level. All presented confidence intervals will be 2-sided 95% confidence intervals.

The SAP will be developed and finalised before database lock and will describe the selection of participants to be included in the analysis and procedures for accounting for unused and spurious data.

11.1.1 Datasets or Populations Analysed

For the purposes of analysis, the following populations are defined for both Parts 1 and 2. Any decisions required for inclusion/exclusion of a population (for example, Per-Protocol Set) will be made for all patients across both Parts 1 and 2.

Population	Description
Enrolled Set	The Enrolled Set will include all participants who sign the ICF.
Randomised Set	The Randomised Set will include all participants who signed the ICF and were subsequently randomised into the study, regardless of study treatment administration.
Full Analysis Set	The Full Analysis Set will serve as the primary population for the analysis of efficacy and will consist of all randomised participants who were administered double-blind study treatment and have an evaluable AF conversion status within 90 min from the start of infusion. Participants will be analysed according to the randomised treatment.

Population	Description
Per-Protocol Set	
The Per-Protocol Set includes all participants from the Full Analysis Set who have been treated according to the protocol and fulfil the following criteria (to be further described in the SAP):
 
 1. All inclusion/exclusion criteria satisfied 2. Absence of relevant protocol violations with respect to factors likely to affect the efficacy of treatment where the nature of protocol violation will be defined before breaking the blind 3. Adequate study drug compliance, which will be determined before breaking the blind 
Participants will be analysed according to the randomised treatment.

Safety Set	All randomised participants who were administered double-blind study treatment. Participants will be analysed according to the treatment received.
PK Set	The PK Set will include all participants in the Safety Set who have at least one evaluable post-baseline drug concentration value.

Abbreviations: AF = atrial fibrillation, ICF = informed consent form, PK = pharmacokinetic, SAP = statistical analysis plan.

11.1.2 Demographic and Other Baseline Characteristics

Descriptive statistical methods will be used to tabulate and summarise demographics and baseline characteristics.

11.1.3 Efficacy Variables

Definition of Primary Efficacy Endpoint

The primary efficacy endpoint is defined as the proportion of patients who have converted from AF within 90 min from the start of infusion, and subsequently have no AF recurrence within 1 min of conversion from AF.

Definition of Secondary Efficacy Endpoints

- The time to conversion from AF from start of infusion.
- The proportion of patients with relapse of AF within 5 min (IRAF) after pharmacological or DC cardioversion.
- The proportion of patients in SR at $3\text{ h} \pm 1\text{ h}$ after start of infusion.
- The proportion of patients in SR at $24\text{ h} \pm 2\text{ h}$ after start of infusion.
- The proportion of patients in SR at $30\text{ days} \pm 5\text{ days}$ after start of infusion.

Methods of Analysis

For the analysis of the primary endpoint (proportion of patients who have cardioversion within 90 min from the start of infusion) a Bayesian model will be utilised. The prior probability of success at a dose, d , is modelled with a $P_d \sim \text{Beta}(1,1)$ prior (uniform) for each dose. Across both Parts 1 and 2 of the study, the potential doses (arms) in the trial are $d = 0$ (placebo), 2, 3, 4, 5, and 6 (all mg/kg dose units).

Let X_d be the number of successes and N_d be the number of observations at dose d . The posterior distribution is calculated for each dose independently using a Beta posterior distribution,

$$P_d \sim \text{Beta}(1 + X_d, 1 + N_d - X_d).$$

The adaptive design utilises the probability that the response rate at a dose is greater than a 65% success rate. This is ($P_d > 0.65$), for each dose d .

This modelling will occur for each interim analysis, and at the final analysis as primary method. At the conclusion of the study, each AP30663 dose will be considered to be superior to placebo, if the posterior probability of AP30663 dose has a higher success rate than placebo is greater than 0.95.

Further to the above, for the final analysis the primary endpoint will also be analysed by means of a logistic regression model. Relevant covariates at baseline may be added into the model after reviewing baseline imbalances.

Secondary endpoints relating to proportions will be analysed using a logistic regression model in a similar manner to that of the primary endpoint. Time to conversion will be analysed using Kaplan-Meier methods and, if met, the median time to conversion will be presented, along with the corresponding Kaplan-Meier plot stratified by treatment group.

Full details of all statistical analyses will be provided in the SAP.

11.1.4 Safety Variables

The safety endpoints are as follows:

- AEs, ECG variables including significant arrhythmia, physical examination, vital signs, and laboratory variables.
- Changes in QTcF interval data over time.

Methods of Analysis

AEs will be coded using the Medical Dictionary for Regulatory Activities (MedDRA). Summaries will be presented by system organ class (SOC) and preferred term. Treatment-emergent AEs (TEAEs) are defined as any AE occurring or worsening on or

after the first dose of study medication. If a participant experiences the same preferred term multiple times, the event will be counted only once overall and by the greatest severity.

The frequency and incidence of TEAEs will be presented by SOC and preferred term for each treatment group (number and percentage of patients experiencing at least one TEAE per preferred term as well as the number of observed events per preferred term). Separate tables will be presented by severity and by relationship, and for SAEs, related TEAEs, and TEAEs leading to study discontinuation. All AEs will be presented in full in a comprehensive listing including participant number, treatment regimen, severity, seriousness, action taken, outcome, relationship to treatment, onset/stop, and duration. Details of SAEs and AEs leading to withdrawal will be listed separately.

For ECG values, a categorical analysis of outliers (e.g. number of ECGs where QTc >450 ms, and QTc >500 ms and change from baseline of >30 ms and >60 ms) will be computed and summarised.

Changes in QTcF intervals over time will be summarised by means of a shift table. Abnormal findings (“normal”, “abnormal, not clinically significant”, and “abnormal, clinically significant”) will be summarised by the number and percentage within each category, and change from baseline will be summarised within shift tables.

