10.6. ECG

A 12-lead digital ECG will be performed at the times outlined in the Study Procedures and Flowchart in Section 3.9 in a standardized manner (*i.e.* after the patient has rested in the [semi]supine position for at least 5 min).

The investigator will assess ECG abnormalities (e.g. ischemia, conduction abnormalities, and rhythm abnormalities) and define the ECG intervals as part of the screening of eligibility and according to the inclusion/exclusion criteria, and as part of an adverse event assessment.

12-lead digital ECG will be overread by the central ECG laboratory. The following measurements will be provided for all PK time points: RR, PR, QRS, QT, QTcF (Fridericia's correction of QT interval), heart rate, as well as T- and U-wave morphology classifications.

Bedside safety ECGs will be collected by the site, printed and reviewed by the investigator on site.

ECG intervals based on these safety ECGs will only be recorded if part of an adverse event.

A summary table for actual and change from baseline will be provided by treatment.

Results for 12-Lead ECGs will be summarized by the number and percentage within each category ("normal", "abnormal, not clinically significant", and "abnormal, clinically significant") .

Abnormal results for 12-Lead ECGs will be summarized as below:

- Absolute QTc interval prolongation:
 - QTc F interval > 450 ms
 - QTc F interval > 500 ms
- Change from baseline in QTc interval:
 - QTc F interval increases from baseline >30 ms
 - QTcF interval increases from baseline >60 ms

ECG data will be listed for all patients, and any clinically significant findings in ECG values will be flagged.

A cardiac Statistical Analysis Plan will be developed by Clario.

This document is confidential.

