 - If Dose d was the largest dose thus far open, and Dose d is < 6 mg/kg, then dose d + 1 will be opened.

The study will continue until all doses of AP30663 have been closed or the maximum of 72 patients during Part 2 (up to 108 patients total across Part 1 and Part 2) have been enrolled.

While the algorithm, and the DMC's decision for dose increase/decrease, is based on AF conversion rate only, the DMC will also convene to review safety and tolerability data at defined time points; review of this data may also lead to further decisions being made by the DMC.

This document is confidential.

12. Changes from Analysis Planned in Protocol

None

This document is confidential.

13. Reference List

None

This document is confidential.

14. Programming Considerations

All tables, figures, listings (TFLs), and statistical analyses will be generated using SAS for Windows, Release 9.4. (SAS Institute Inc., Cary, NC, USA). Computer-generated table, listing and figure output will adhere to the following specifications.

The static analysis based on plasma concentration will be performed using a non-compartmental analysis (NCA), the PK analyses will be performed by Syneos Health using Phoenix WinNonlin® (release 8.0 or higher) and all other analyses and summaries will be produced using Statistical Analysis System (SAS®) version 9.4 (or higher).

PK analyses will be performed using NONMEM® version 7.4.

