Table 14.3.1.6	Treatment-Emergent Adverse Events by System Organ Class, Preferred Term, and Maximum Severity	Safety Set	
Table 14.3.4.1.1.1	Summary statistics of Laboratory Data: Haematology	Safety Set	
Table 14.3.4.1.1.2	Change from Baseline in Laboratory Data: Haematology	Safety Set	
Table 14.3.4.1.1.3	Laboratory Data: Haematology Relationship to Reference Range – Shift from Baseline	Safety Set	

This document is confidential.

Table Number	Name	Analysis Set	Delivered for Interim analysis/DMC
Table 14.3.4.1.1.4	Laboratory Data: Haematology Clinical Significance	Safety Set	
Table 14.3.4.1.2.1	Summary statistics of Laboratory Data: Clinical Chemistry	Safety Set	
Table 14.3.4.1.2.2	Change from Baseline in Laboratory Data: Clinical Chemistry	Safety Set	
Table 14.3.4.1.2.3	Laboratory Data: Clinical Chemistry Relationship to Reference Range – Shift from Baseline	Safety Set	
Table 14.3.4.1.2.4	Laboratory Data: Clinical Chemistry Clinical Significance	Safety Set	
Table 14.3.4.2.1	Summary of Vital Signs	Safety Set	
Table 14.3.4.2.2	Change from Baseline in Vital Signs	Safety Set	✓
Table 14.3.4.3.1	Summary of 12-Lead ECG Parameters	Safety Set	
Table 14.3.4.3.2	Change from Baseline in 12-Lead ECG Parameters	Safety Set	✓
Table 14.3.4.3.3	12-Lead ECG Clinical Significance	Safety Set	✓
Table 14.3.4.3.4	12-Lead ECG QTc Intervals: Categorical Analysis	Safety Set	✓
Table 14.3.4.4	Brief Physical Examination - Shift from Baseline	Safety Set	

This document is confidential.

17. Index of Figures

Figure Number	Figure Title	Delivered for Interim analysis/DMC
Figure 14.2.2.1.3	Kaplan-Meier curve for Time to Conversion from AF – Full analysis set	
Figure 14.2.3.3	Mean (\pm SD) Plasma Concentration - Linear and Semi-Log Scales - PK Set	✓ For interim analysis this graph will be provided by the PK group
Figure 14.2.3.4	Overlay of Individual and Mean AP30663 Plasma Concentrations by Treatment - Linear and Semi-Log Scales - PK Set	✓ For interim analysis this graph will be provided by the PK group
Figure 14.2.3.5	Scatter plot of Plasma Concentration Immediately After Conversion versus Time to Conversion – PK set	
Figure 14.2.3.6	Mean (\pm SD) Cmax vs. AP30663 Dose Level - PK Set	
Figure 14.2.3.7	Mean (\pm SD) AUC0-t vs. AP30663 Dose Level - PK Set	
Figure 14.2.3.8	Mean (\pm SD) AUC0-0.5 vs. AP30663 Dose Level - PK Set	
Figure 14.2.3.9	Scatter Plot of Cmax vs. Time to Conversion - PK Set	
Figure 14.2.3.10	Scatter Plot of AUC0-t vs. time to conversion- PK Set	

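### The SAP omits both ECG shift tables planned in the protocol without declaring it, so the by-arm summary of ECG findings loses its link to baseline

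*Protocol*

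**What the plan says.** Protocol 11.1.4 (Safety Variables) describes two shift presentations for ECG data. The first is for QTcF: "Changes in QTcF intervals over time will be summarised by means of a shift table". The second follows directly and concerns the three-level classification of findings (normal; abnormal, not clinically significant; abnormal, clinically significant). Each level is to be counted, "and change from baseline will be summarised within shift tables".

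SAP 10.6 (ECG) carries over the counting half of that second plan: "Results for 12-Lead ECGs will be summarized by the number and percentage within each category". It says nothing about a shift. For the measured ECG parameters it adds: "A summary table for actual and change from baseline will be provided by treatment". It also keeps the QTcF outlier categories (above 450 and 500 ms; increases above 30 and 60 ms) and a by-patient listing with clinically significant findings flagged. It mentions that the ECG vendor will write a separate cardiac SAP.

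The index in SAP Section 16 has four ECG tables, 14.3.4.3.1 to 14.3.4.3.4. The one for the finding categories is 14.3.4.3.3, titled "12-Lead ECG Clinical Significance" and marked for interim/DMC delivery. None of the four is a shift table. Under the heading "12. Changes from Analysis Planned in Protocol", the SAP's whole entry is the single word None.

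**The concern.** A safety analysis named in the protocol is missing from the SAP, and the section meant to record such differences says there are none. That alone needs correcting.

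The second issue is what the remaining table can show. Patients are infused while in AF, which Protocol 9.2 requires to be confirmed on the pre-infusion 12-lead ECG, so abnormal baseline tracings are to be expected. Two things can then change a patient's category after infusion: conversion can remove an abnormality, and a new finding can add one. Counts per category that are not linked to the same patient's baseline can let these movements offset each other within an arm. A shift table shows each movement separately, which is presumably why the protocol planned one.

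**Working it through.** No figure in the plan can be recomputed, so the check is a comparison of texts followed by a simple bound.

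**Step 1: plan against SAP.**

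| Item | Protocol 11.1.4 | SAP text | SAP Section 16 |
|---|---|---|---|
| QTcF over time | Shift table | 10.6: actual and change from baseline by treatment; >450, >500, +30, +60 ms | 14.3.4.3.1, 14.3.4.3.2, 14.3.4.3.4; no shift table |
| Three ECG categories | Counts and shift tables | 10.6: counts and percentages only | 14.3.4.3.3; no shift table |
| Laboratory (for contrast) | – | 10.4: shift from baseline | 14.3.4.1.1.3 and 14.3.4.1.2.3 |
| Physical examination (for contrast) | – | 10.7: shift tables | 14.3.4.4 |

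Both ECG shift tables are absent, while the SAP specifies and indexes the same type of table for laboratory and physical examination data. The None in Section 12 is therefore incorrect.

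**Step 2: does the QTcF omission hide new prolongation?** Exclusion criterion 16 caps QTcF at 450 ms at randomisation, and Protocol 9.2 bars infusion above 450 ms. Apart from deviations and differences between site and central readings, a shift table cut at 450 and 500 ms would have one baseline row. It would then equal the one-way outlier table that the SAP keeps. The +30 and +60 ms categories are already relative to baseline. So new prolongation stays identifiable.

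**Step 3: what do unpaired category counts leave open?** Let n be the arm size, a the number clinically significant at baseline and b the number clinically significant after infusion. The number newly significant lies between max(0, b − a) and min(b, n − a). Protocol 17.3 shows an active arm of n = 12 at the first Part 2 interim with one dose open. The values of a and b below are assumed, since the documents give none, and Table 14.3.4.3.3 is assumed to show both margins.

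| n | a | b | Lower bound | Upper bound | Newly significant |
|---|---|---|---|---|---|
| 12 | 0 | 6 | max(0, 6) = 6 | min(6, 12) = 6 | exactly 6 |
| 12 | 6 | 6 | max(0, 0) = 0 | min(6, 6) = 6 | 0 to 6 (0% to 50%) |
| 12 | 12 | 6 | max(0, −6) = 0 | min(6, 0) = 0 | exactly 0 |
| 18 | 9 | 9 | max(0, 0) = 0 | min(9, 9) = 9 | 0 to 9 (0% to 50%) |

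The ambiguity arises only when baseline categories are mixed. If AF puts every patient in the same category, the shift table has one row and adds nothing to the counts. The documents do not say how AF is to be classified, so neither case can be ruled out.

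**Step 4: would the protocol's table be enough?** Only partly. If AF is coded clinically significant, a patient with persisting AF and a patient with persisting AF plus a new conduction disorder both fall in the significant-to-significant cell. A three-category shift table cannot separate them unless AF rhythm is shown apart from other abnormalities.

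**The case against.** A reader might infer that, under this SAP, new ECG abnormalities cannot be told from pre-existing ones, or that the DMC would not see them. The documents do not support that:

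- Listing 16.2.8.3 (12-lead ECG) is marked for interim/DMC delivery and keeps each patient's pairing. The arms in the protocol's examples have 6 to 36 active patients, so it can be read by hand.
- Table 14.3.4.3.2, change from baseline in ECG parameters, is also marked for the DMC. PR and QRS are among the measured parameters and bear directly on conduction.
- QRS above 120 ms, known AV block and complete bundle branch block are exclusions, so the conduction disorders most likely to confuse the picture should be rare at baseline.
- Conversion and sinus rhythm by time point have their own tables for the DMC. Treatment-emergent adverse events are new or worsening by definition.
- The cardiac SAP, which is not among the documents reviewed, may contain the QTcF shift table.
- The protocol does not promise a shift table at interims, and the dose algorithm uses conversion only.

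All of this stands, and it limits the consequence. It does not make the Section 12 entry correct. A listing is also not the by-arm summary that the protocol planned. If the cardiac SAP holds the tables, this SAP does not say so, although the protocol (in 11.1.3) states: "Full details of all statistical analyses will be provided in the SAP". The retained QTcF tables cover prolongation, but SAP 10.6 names no time points for the change-from-baseline summary, whereas the protocol's shift table was explicitly over time.

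**Conclusion.** The omission is real and undeclared: both ECG shift tables in Protocol 11.1.4 are missing from SAP 10.6 and Section 16, and Section 12 wrongly reports no change. The consequence is confined to the by-arm summary of ECG findings. Table 14.3.4.3.3 does not show how many patients moved into the clinically significant category when baseline categories are mixed.

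The size cannot be fixed from the documents. In the illustration it ranges from no loss (all patients in one baseline category) to an uncertainty of half the arm (6 of 12, under assumed margins). The upper figure is a bound under invented counts, not an expected error.

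Severity is minor to moderate: a safety-reporting gap with no effect on the primary analysis or the dose algorithm. This rests on two assumptions. The first is that the three categories in the protocol sentence refer to ECG findings, as SAP 10.6 itself applies them. The second is that no other document already supplies the tables.

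**What to change.** 1. In SAP 10.6 and Section 16, restore the ECG-category shift table from baseline to each post-infusion time point, by arm. State how AF is classified, and show AF rhythm separately from other abnormalities so that a new finding in a patient still in AF is visible.
2. Restore the QTcF shift table with defined categories and time points, or cross-refer to the cardiac SAP if the table is there. Cut-offs at 450 and 500 ms alone would add little to the existing outlier table.
3. Replace None in SAP Section 12 with an entry and a reason for anything deliberately dropped.

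Marking the category shift table for the DMC beside 14.3.4.3.3 is optional. The cost is one or two tables of a type already planned for laboratory and physical examination data, plus a short text edit. No new data collection should be needed if rhythm is taken from the ECG data already recorded.
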